2.2 RATIONALE

Study Part 2: This pilot study will establish baseline carriage prevalence in 500 first year university students. Very few students will have previously been vaccinated with a MenB vaccine as this study will be conducted prior to Phase 1. The findings will assist in validation of study processes for Phase 1, particularly laboratory processes. A follow up swab taken 3 months later will provide data on the change in carriage that may occur over this 3 month period. Study Part 3 will evaluate carriage rates following introduction of a meningococcal B vaccine program, compare carriage rates in vaccinated and unvaccinated individuals and determine risk factors for carriage prevalence of *N. meningitidis* genogroups causing disease in South Australian school leavers. School leavers are defined as students who were enrolled in year 12 at school in the preceding year of recruitment and have been chosen as they are likely to have the highest carriage rates. Following completion of Phase 1, a high proportion (approximately two thirds) of students will be immunised by the time of throat swab collection in years 2018 and 2019. Assessing carriage in both vaccinated and unvaccinated cohorts will further inform the effect the 4CMenB vaccine has on carriage at a population level. This will help inform national immunisation program funding of 4CMenB vaccine in adolescents in Australia and internationally.

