3 OBJECTIVES AND PURPOSE

Pilot Study Part 2: Longitudinal Carriage Study

Primary Objective

• Estimate the carriage prevalence of all genogroups of *N. meningitidis* in South Australian first year university students.

Secondary Objectives

- Estimate the carriage prevalence of *N. meningitidis* genogroups causing disease (*A*, *B*, *C*, *W*, *X*, *Y*) in South Australian first year university students.
- Identify characteristics associated with carriage prevalence of all *N. meningitidis* genogroups in South Australian first year university students.
- Estimate the change in carriage prevalence of all genogroups of *N. meningitidis* in South Australian first year university students at baseline (first week of university) and 3 months later.
- Estimate any difference in PCR positivity after freezing of the sample at 6, 16 and 48 hours post collection.
- Estimate any difference in positivity of isolates determined by culture after freezing of samples at 6, 16 and 48 hours post collection

Study Part 3: Cross-sectional Carriage Study

Primary Objective

• Estimate the difference in carriage prevalence of disease causing genogroups of *N.meningitidis (A, B, C, W, X, Y)* in South Australian school leavers in 2018 (year 12 in 2017),2019 (year 12 in 2018) and 2020 (year 12 in 2019)following implementation of a school immunisation program in year 10, 11 and 12 South Australian students from 2017-2018.

Secondary Objectives

• Estimate the difference in carriage prevalence of all N. *meningitidis* genogroups in South Australian school leavers in 2018 (year 12 in 2017), 2019 (year 12 in 2018) and 2020 (year 12 in 2019) following implementation of a school immunisation program in year 10, 11 and 12 South Australian students from 2017-2018.

- Estimate the difference in carriage prevalence of each N. *meningitidis* genogroup (*A*, *B*, *C*, *W*, *X*, *Y*) in South Australian school leavers in 2018 (year 12 in 2017), 2019 (year 12 in 2018) and 2020 (year 12 in 2019) following implementation of a school immunisation program in year 10, 11 and 12 South Australian students from 2017-2018.
- Estimate the difference in carriage prevalence of all N. meningitidis genogroups in South Australian school leavers who have received Bexsero [®] compared to unvaccinated students.

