9 STATISTICAL CONSIDERATIONS

9.1 DESCRIPTION OF STATISTICAL METHODS

9.1.1 GENERAL APPROACH

Logistic regression with adjustment for confouding will be used to identify factors associated with carriage and to compare carriage rates annually and between vaccinated and unvaccinated students. Changes in carriage between baseline and 3 months later will be evaluated using logistic regression with generalised estimating equations. In all analyses of carriage prevalence, effects will be described using odds ratios with 95% confidence intervals.

For comparing the difference in PCR +ve samples after freezing of the sample at 6 hours and 48 hours, we will compare paired proportions using a logistic model with generalised estimating equations, and assess agreement using a Kappa statistic.

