2. STUDY METHODS

2.1 Overall study design

Observational cross sectional study of South Australian school leavers in 2018 and 2019.

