5. SAMPLE SIZE ESTIMATION

Assuming the carriage prevalence of disease associated genogroups of *N. meningitidis* (A, B, C, W, X, Y) in school leavers in 2018 is 8%, a sample size of 4,096 students per year will provide 80% power to detect a 20% relative reduction in carriage prevalence between 2018 and 2019 (two tailed alpha = 0.05).

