6.2 Adjustment

Adjustment will be made for risk factors that had a two-tailed p-value < 0.05 in the multivariable model for baseline disease-causing carriage in the High School B Part of It RCT (see <https://clinicaltrials.gov/ct2/show/NCT03089086> for description of study). These include current cold or sore throat (no, yes), smoking cigarettes (no, yes), smoking water pipes (no, yes), days out at a pub/club in last week (0, 1 or more), people kissed in last week (0, 1 or more), and ethnicity (Caucasian, Asian, Aboriginal or Torres Strait Islander, Other). Adjustment will also be made for alcohol consumption in the last month (no, yes), as this emerged as an important risk factor

for disease-causing carriage in a preliminary analysis of 2018 School Leaver data. Previous vaccination with MenACWY (no, yes) and participation in the High School B Part of It RCT (no, yes) will also be considered for inclusion in the adjusted model. In order to address each hypothesis, both unadjusted and adjusted analyses will be performed, with primary conclusions to be based on the results of adjusted analyses. No adjustment will be made for risk factors in the analysis of carriage of genogroups A, C, W and X, as only small numbers of cases are expected to be detected.

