6.5 Secondary Outcomes

6.5.1 Carriage prevalence of all genogroups of *N. meningitidis* in school leavers in 2018 compared to 2019

Outcome: Binary outcome based on the presence of any *N. meningitidis*

(groupable or non-groupable) by PCR.

Effect: Odds ratio for all genogroups of *N. meningitidis* (2018 vs 2019).

Analysis: Test for a difference using logistic regression. Adjustment will be conducted as described in 6.2.

6.5.2 Carriage prevalence of each individual group of *N. meningitidis* (A, B, C, W, X, Y, and non-groupable) in school leavers in 2018 compared to 2019

Outcome: Binary outcomes (one for each group) based on the presence of specific meningococcal DNA by PCR for genogroups A, B, C, W, X, Y and non-groupable.

Effect: Odds ratio for *N. meningitidis* carriage for each genogroup (2018 vs 2019).

Analysis: Test for a difference using logistic regression. Adjustment will be conducted as described in 6.2.

6.5.3 Carriage prevalence of disease-causing genogroups of *N. meningitidis* (A, B, C, W, X, Y) in vaccinated compared to unvaccinated school leavers

Outcome: Binary outcome based on the presence of at least one disease-causing genogroup of *N. meningitidis* (A, B, C, W, X, Y) by polymerase chain reaction (PCR).

Effect: Odds ratio for disease-causing genogroups of *N. meningitidis* (4CMenB Vaccinated vs 4CMenB Unvaccinated).

Analysis: Test for a difference using logistic regression. Adjustment will be conducted as described in 6.2.

6.5.4 Carriage prevalence of all *N. meningitidis* in vaccinated compared to unvaccinated school leavers

Outcome: Binary outcome based on the presence of any *N. meningitidis* (groupable or non-groupable) by polymerase chain reaction (PCR).

Effect: Odds ratio for any *N. meningitidis* (4CMenB Vaccinated vs 4CMenB Unvaccinated).

Analysis: Test for a difference using logistic regression. Adjustment will be conducted as described in 6.2.

6.5.5 Carriage prevalence of each individual group of *N. meningitidis* (A, B, C, W, X, Y, and non-groupable) in vaccinated compared to unvaccinated school leavers

Outcome: Binary outcome (one for each group) based on the presence of *N. meningitidis* (groupable and non-groupable) by PCR.

Effect: Odds ratio for each individual genogroup of *N. meningitidis* (4CMenB Vaccinated vs 4CMenB Unvaccinated).

Analysis: Test for a difference using logistic regression. Adjustment will be conducted as described in 6.2.

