6.5.6 Carriage prevalence of disease-causing genogroups of *N. meningitidis* (A, B, C, W, X, Y) among vaccinated school leavers by timing of vaccination

Outcome: Binary outcome based on the presence of at least one disease-causing genogroup of *N. meningitidis* (A, B, C, W, X, Y) by polymerase chain reaction (PCR).

Effect: Odds ratio for disease-causing genogroups of *N. meningitidis* for each additional month since vaccination (based on receipt of the 2nd dose).

Analysis: Test for an association using logistic regression, with months since vaccination treated as a continuous variable. Adjustment will be conducted as described in 6.2.

6.5.7 Carriage prevalence of all genogroups of *N. meningitidis* among vaccinated school leavers by timing of vaccination

Outcome: Binary outcome based on the presence of any *N. meningitidis* (groupable or non-groupable) by polymerase chain reaction (PCR).

Effect: Odds ratio for any *N. meningitidis* for each additional month since vaccination (based on receipt of the 2nd dose).

Analysis: Test for an association using logistic regression, with months since vaccination treated as a continuous variable. Adjustment will be conducted as described in 6.2.

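### SAP 6.5.3 to 6.5.7 combine 2018 and 2019 with no term for year, so a secular change in carriage can pass into the vaccine and time-since-dose odds ratios

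*SAP*

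**What the plan says.** SAP 2.1 describes an "Observational cross sectional study of South Australian school leavers in 2018 and 2019". SAP 6.5.3 to 6.5.5 define one odds ratio per outcome for vaccinated against unvaccinated students. SAP 6.5.6 and 6.5.7 define one odds ratio among the vaccinated "for each additional month since vaccination (based on receipt of the 2nd dose"). The SAP does not say in words that the two years are combined, but a single odds ratio over a two-year study implies it.

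Each of these sections refers to SAP 6.2 for adjustment and to nothing else. The rule there is: "Adjustment will be made for risk factors that had a two-tailed p-value < 0.05 in the multivariable model for baseline disease-causing carriage", meaning the baseline model of the earlier school trial. It yields cold or sore throat, cigarettes, water pipes, pub or club days, people kissed and ethnicity. Alcohol is added from a preliminary look at 2018 data. MenACWY vaccination and participation in the school trial are to be considered. Genogroups A, C, W and X are left unadjusted. Recruitment year appears only as the exposure in 6.4.1, 6.5.1 and 6.5.2 and as the grouping in the 4.1 table.

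Protocol 9.1.1 states in general terms that "adjustment for confouding will be used to identify factors associated with carriage and to compare carriage rates annually and between vaccinated and unvaccinated students", but it names no covariates.

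**The concern.** Year confounds these analyses if it is related both to carriage and to the exposure.

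The first link is one the plan itself takes seriously, since the study is sized for "80% power to detect a 20% relative reduction in carriage prevalence between 2018 and 2019". The selection rule in 6.2 cannot bring year in, because its sources are a different study and 2018 data alone.

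The second link differs between the two sets of analyses:

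- **Months since dose 2 (6.5.6, 6.5.7).** Protocol 3 describes "implementation of a school immunisation program in year 10, 11 and 12 South Australian students from 2017-2018", and Protocol 5.3 places swabs in February to June. A student swabbed in 2019 may have had dose 2 in 2017 or 2018, whereas one vaccinated in the programme and swabbed in 2018 had it more recently. Long intervals should therefore fall mostly in the 2019 cohort. A secular fall in carriage would mask waning, and a rise would mimic it.
- **Vaccinated against unvaccinated (6.5.3 to 6.5.5).** This depends on coverage by year, which is not given. Protocol 2.2 says only that "a high proportion (approximately two thirds) of students will be immunised by the time of throat swab collection in years 2018 and 2019". Protocol 5.3 mentions year 12 students in Group B who still had two doses to come, so coverage could differ, but the size is unknown. If coverage is higher in 2019, a secular fall makes a null vaccine look protective and a rise makes it look harmful.

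**Working it through.** **Inputs from the documents.** Carriage of 8% in 2018, a 20% relative change, 4,096 per year and two-sided alpha 0.05 (SAP 5); coverage of about two thirds (Protocol 2.2); swabs February to June (Protocol 5.3). **Assumed:** coverage by year, dose-2 dates, and the 20% fall (8.0% to 6.4%) taken as a secular change.

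**The plan's own figure.** With p̄ = 0.072, n = [1.96√(2·0.072·0.928) + 0.842√(0.08·0.92 + 0.064·0.936)]² / 0.016² = 4,096 per year, as stated. The year odds ratio (2019 v 2018) is (0.064/0.936)/(0.08/0.92) = 0.786, log −0.240.

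**1. Vaccinated v unvaccinated, null vaccine.** With coverage c and carriage p by year:

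- pV = (c18·p18 + c19·p19)/(c18 + c19)
- pU = [(1−c18)·p18 + (1−c19)·p19]/(2 − c18 − c19)

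Example, 50%/83%: pV = (0.0400 + 0.0531)/1.33 = 0.0700 and pU = (0.0400 + 0.0109)/0.67 = 0.0759, so OR = 0.0753/0.0822 = 0.916. With 4,096 × 1.33 = 5,448 vaccinated and 4,096 × 0.67 = 2,744 unvaccinated, SE = √(1/354.8 + 1/192.6) = 0.0895 and z = −0.98. The chance of p < 0.05 is Φ(−0.98) + Φ(−2.94) = 16% to 17%.

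| Coverage 2018/2019 | 20% fall | 10% fall | 20% rise |
|---|---|---|---|
| 67%/67% | 1.00 (5%) | 1.00 (5%) | 1.00 (5%) |
| 60%/73% | 0.97 (7%) | 0.98 (5%) | 1.03 (6%) |
| 57%/77% | 0.95 (9%) | – | – |
| 50%/83% | 0.92 (16–17%) | 0.96 (8%) | 1.08 (15%) |

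Cells are the expected OR and, in brackets, the false-positive rate. With year in the model the expected OR is 1.00 throughout.

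**2. Months since dose 2, no true waning, 20% fall.** There are 2,731 vaccinated per year (two thirds of 4,096). Dose-2 timings assumed:

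- A: 2018 cohort June–August 2017; 2019 cohort half June–August 2017, half April–June 2018
- B: as A, but one quarter and three quarters
- C: 2018 cohort uniform June–December 2017; 2019 cohort uniform June 2017–December 2018

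Hand approximation for A. Mean months since dose 2 are 9 (2018) and 16 (2019).

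- Variance in 2018: 5²/12 (swab) + 3²/12 (dose) = 2.83. In 2019: 2.83 + 0.25·10² = 27.83. The average within-year variance is 15.33.
- Total variance: 15.33 + 7²/4 = 27.58.
- Slope of year on months: (7/4)/27.58 = 0.0634 per month, or 0.761 per 12 months.
- Leaked log OR: 0.761 × (−0.240) = −0.183, so OR ≈ 0.83 per 12 months.
- Variance inflation from adding year: 27.58/15.33 ≈ 1.8.

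Simulation, 600 runs each, OR per 12 months:

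| Timing | Without year (p < 0.05) | With year (p < 0.05) | Variance ratio | True OR 1.20: without / with year |
|---|---|---|---|---|
| A | 0.823 (34%) | 1.001 (6%) | 1.84 | 0.986 / 1.187 |
| B | 0.822 (22%) | 0.997 (5%) | 1.41 | 0.987 / 1.189 |
| C | 0.849 (25%) | 0.993 (6%) | 1.51 | 1.031 / 1.213 |

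Large-sample fits agree (0.828, 0.822, 0.855). In the SAP's unit, 0.82 to 0.85 per 12 months is 0.984 to 0.987 per month (twelfth root). A 10% fall gives 0.91 to 0.93 per 12 months (9% to 12%). A 20% rise gives 1.13 to 1.16 (20% to 29%).

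**Extreme case.** If all second doses fell in June–August 2017, the yearly means are 9 and 21 months and the variance inflation is (2.83 + 12²/4)/2.83 ≈ 13.7 (13.6 from the fit). The model without year gives 0.80 per 12 months (59%).

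**The case against.** The omission and the arithmetic are not in dispute. The case on the other side concerns reach and size.

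- **No bias is shown for 6.5.3 to 6.5.5.** If the two-thirds figure holds in each year, the bias is nil. Moderate gaps give 0.95 to 0.97. This stands: for these sections the year term is a precaution.
- **The 20% is a design target after a vaccine programme, not an estimate of drift.** This also stands. At 10% the months analysis is still biased, but less (0.91 to 0.93 per 12 months).
- **Dose timing is inferred.** It is: no dose-2 dates are given, and SAP 6.1 also admits vaccination confirmed by providers outside the school trial. The three timings show a range and do not predict the data.
- **The fix leaves an imprecise answer.** With year included, the SE of the log OR per 12 months is 0.149 to 0.187. The 95% interval is then the estimate times or divided by 1.34 to 1.44 (e^(1.96·SE)), and power for a true 1.20 is about 18% to 24%. That is right, but a wide unbiased interval reports the evidence better than a narrower biased one.
- **The outcomes are exploratory, and SAP 4.1 would reveal an imbalance.** SAP 6.3 does call them exploratory, yet each is tested at 0.05, and Protocol 2.2 expects the comparison of vaccinated and unvaccinated students to inform funding decisions. A table shows an imbalance but does not remove its effect.

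Participation in the school trial does not stand in for year, and it is only to be considered.

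**Conclusion.** The concern holds and should be fixed. SAP 6.5.3 to 6.5.7 leave out recruitment year, and nothing in SAP 6.2 or Protocol 9.1.1 brings it in.

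The case is strongest for 6.5.6 and 6.5.7, where the programme dates make time since dose 2 likely to differ by year. Under the planned 20% fall and the assumed timings, the model without year cancels a true waning odds ratio of 1.20 per 12 months almost completely. For 6.5.3 to 6.5.5 the bias ranges from none to an odds ratio of about 0.92, depending on a coverage gap that the documents do not give.

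Confidence is high that year is omitted and in the direction of the bias, given how exposure differs by year. The sizes are conditional on the assumptions stated. The primary analysis is unaffected because year is its exposure, and the sample size is unchanged.

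**What to change.** In SAP 6.2, state that recruitment year (2018, 2019) is a covariate or stratum in 6.5.3 to 6.5.7. For genogroups A, C, W and X, do this only where counts allow. Naming year in the Section 7 multivariable models would be consistent; that section fixes no covariate list, so this is an addition and not a correction.

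SAP 4.1 already compares MenB vaccine status, split at 12 months since dose 2, between the years. Add the mean and range of months since dose 2 by year. State in advance that if months and year nearly coincide, their effects will be reported as not separable.

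The cost is one sentence, one variable already recorded and one table row. The variance of the vaccine effect in 6.5.3 rises by 0% to about 13% over the coverages shown. The variance of the months effect rises about 1.4 to 1.9 fold, or about 14 fold in the extreme timing, where the data could not usefully separate the two effects.

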Data in relation to carriage in Australia are scant and very little is known about overall carriage prevalence of *Neisseria meningitidis* (i.e. all strains), or the proportion of strains that are meningococcal serogroup B. The only Australian data available in the literature reporting 1.7% carriage were from a sample of 294 school aged children of various ages in Queensland and was conducted in 1989.(12) The improvement in sensitivity of newer molecular diagnostic techniques and the fact that South Australia regularly reports higher Invasive Meningococcal Disease rates than Queensland leads us to suspect that baseline carriage in South Australian adolescents will be higher than 1.7%. In carriage studies conducted in Europe, carriage prevalence was estimated at 4-5% in infants to a peak of 23-7% in 19-year olds. Recently presented carriage rates from Nottingham University in the UK ranged from 14.3% - 46.2% for all serogroups at the commencement of the university year and 6 months later.[Oldfield N et al. IPNC Mancester, UK, September 2016] Carriage rates for serogroup B ranged from 3.3% to 8.5% over the same time period. As no carriage data exist in Australia since commencement of the meningococcal C vaccine program, we will conduct a longitudinal pilot study of 500 first year university students during orientation week in 2017 at the University of Adelaide (Study Part 2). These students will undergo a posterior pharyngeal swab and complete a short questionnaire to collect information about possible risk factors at the beginning of university and then 3 months later.

Age is one the most important factors influencing carriage, with peak carriage occurring around 18- 19 years of age. Other factors that influence carriage are being male, concomitant respiratory infections, active and passive smoking, number and closeness of social contacts, and low socioeconomic status.(6) Disease is a rare outcome of infection (5) but the relationship between carriage and disease incidence is not fully understood. With carriage rates significantly higher in adolescents, a reduction in carriage in this group has the potential to provide protection to unvaccinated people (herd immunity), including infants.

Study Part 3: Cross-sectional carriage study

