5.3 STRATEGIES FOR RECRUITMENT

Study Part 2: In 2017, university students from The University of Adelaide will be approached to be involved in the study. The sampling frame will occur during orientation week and 500 students will be recruited to provide posterior oro-pharyngeal swabs. Students will be provided with a \$20 iTunes voucher to reimburse their time for each visit.

Study Part 3: Adelaide's three largest universities (The University of Adelaide, University of South Australia, and Flinders University) will be approached to be involved in the study in 2018 and 2019 and potentially 2020. All school leavers aged between 18-25 years will be invited to enrol in the study by use of advertising in the university and distribution of postcards and through council immunisation clinics in 2018. Year 12 students in Group B who will be returning for 2 doses of Bexsero will be provided with a letter and SMS text message reminding them of their vaccinations that are due and the opportunity to further participate with an additional throat swab. At the end of each year a letter will be provided to schools to distribute to all students in year 12 to invite their participation for a throat swab the following year. An Enrolled Nurse, Registered Nurse, or Medical Officer will collect a posterior pharyngeal swab from all enrolled students. We will be aiming to recruit 4096school leavers from February – June each year.. The student will be required to fill out a questionnaire and provide a one off posterior pharyngeal swab. The survey will collect information on potential risk factors (prior vaccination, smoking history, household size, recent antibiotic use) for the carriage of N. meningitidis. No ongoing visits are required. Participants will be offered a \$40 voucher to compensate them for travel expenses.

A communications officer will be employed to work with university students union and public relations to advertise the study to university students at all 3 universities on establishing appropriate and accessible avenues of communication. Involving students in the planning and delivery of communication strategies is expected to facilitate two way communication and provide opportunities for students to engage in research.

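### SAP 6.2 chooses covariates mainly by p-value in another study and omits sex, other smokers at home, age and recent antibiotics, so residual confounding is possible in the vaccinated-versus-unvaccinated comparisons

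*SAP*

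**What the plan says.** SAP 6.2 sets one adjustment rule for the primary and secondary comparisons: "Adjustment will be made for risk factors that had a two-tailed p-value < 0.05 in the multivariable model for baseline disease-causing carriage", the model being that of the high school RCT. The list begins "These include current cold or sore throat (no, yes), smoking cigarettes (no, yes), smoking water pipes (no, yes" and continues with pub or club visits, kissing and ethnicity. Alcohol is added because of a preliminary look at the 2018 school leaver data. MenACWY vaccination and RCT participation "will also be considered for inclusion in the adjusted model". Genogroups A, C, W and X are not adjusted. Unadjusted results are also produced, with "primary conclusions to be based on the results of adjusted analyses".

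The protocol's own account of carriage is in section 2.1: "Age is one the most important factors influencing carriage", and "Other factors that influence carriage are being male, concomitant respiratory infections, active and passive smoking". Section 5.3 says the survey covers "potential risk factors (prior vaccination, smoking history, household size, recent antibiotic use", among others. Section 9.1.1 commits to adjusting for confounding when comparing years and when comparing vaccinated with unvaccinated students.

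Sex, age, other smokers at home and antibiotic use (four levels) all appear in the SAP 4.1 baseline table. None of them is in the list in 6.2.

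**The concern.** A confounder is related both to the outcome and to the exposure. A p-value for carriage in another sample addresses only the first half. It does so imperfectly, because a factor that misses 0.05 can still bias a comparison if it differs enough between the groups.

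For 2018 v 2019 this may matter little if the two intakes are alike. The same set, however, serves SAP 6.5.3 to 6.5.5, where exposure is vaccination status. Protocol 2.1 describes the comparison group as including people who did not wish to be vaccinated. Protocol 5.3 shows that some students had to return for their doses. SAP 6.1 also covers leavers who were never in the RCT. Vaccination status is therefore partly self-selected, and differences by sex or household are plausible. Conclusions rest on the adjusted estimates, so the covariate list carries weight. Protocol 2.2 says the results are meant to inform vaccine funding.

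**Working it through.** **1. The plan's own figure.** Inputs from SAP 5: 8.0% in 2018, a 20% relative reduction (so 6.4% in 2019), 80% power, two-sided 0.05. Using the pooled-variance formula for two proportions:

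n = [1.960 × √(2 × 0.072 × 0.928) + 0.842 × √(0.08 × 0.92 + 0.064 × 0.936)]² / 0.016² = 4,096 per year.

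This matches the plan exactly and does not depend on the covariate set. The planned contrast is an odds ratio of (0.064/0.936)/(0.08/0.92) = 0.79.

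**2. Named, collected, adjusted for?**

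| Factor | Protocol status | In SAP 4.1 | In SAP 6.2 list |
|---|---|---|---|
| Sex | influences carriage (2.1) | yes | no |
| Passive smoking / smokers at home | influences carriage (2.1) | yes | no |
| Age | influences carriage (2.1) | yes | no |
| Recent antibiotics | potential risk factor (5.3) | yes | no |

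**3. Possible size of bias from sex.** With no vaccine effect, the ratio of carriage, vaccinated to unvaccinated, is (1 + (k − 1)m₁)/(1 + (k − 1)m₀). Here k is the male-to-female carriage ratio, and m₁ and m₀ are the male shares in the vaccinated and unvaccinated. The documents give none of these, so all are assumptions.

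- k = 1.5, 45% v 55% male: 1.225/1.275 = 0.96
- k = 2, 40% v 60% male: 1.40/1.60 = 0.875

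Reversing the imbalance gives the reciprocals, 1.04 and 1.14. With equal shares the ratio is 1.

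**4. The other factors, by the same formula and also on assumed inputs.**

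- Smokers at home: ratio 1.2 to 2.0, 20% of vaccinated v 25–30% of unvaccinated, giving 1.04/1.05 = 0.99 to 1.2/1.3 = 0.92.
- Antibiotics: ratio 0.7 to 0.3, 10–12% of vaccinated v 5–10% of unvaccinated, giving 0.964/0.97 = 0.99 to 0.93/0.965 = 0.96.

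**5. Scale against sampling error.** Take 8,192 leavers, two thirds vaccinated (Protocol 2.2) and mean carriage of 7.2%. The standard error of the log odds ratio is √[(1/5,461 + 1/2,731)/(0.072 × 0.928)] ≈ 0.09. The two sex scenarios are then shifts of about 0.4 and 1.5 standard errors. Treating the prevalence ratio as the odds ratio, a nominal 5% false-positive rate would become about 7% and 31%. This assumes that the existing covariates absorb none of the bias.

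**6. Can the model carry the additions?** Expected carriers of disease-causing genogroups over two years: 4,096 × 0.08 + 4,096 × 0.064 = 328 + 262 = 590.

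- Current parameters: 9 listed (ethnicity counts 3), 2 optional and 1 exposure, so 12. 590/12 ≈ 49 carriers per parameter.
- Additions: sex 1, smokers at home 1, age 1, antibiotics 3, so 6. 590/18 ≈ 33 per parameter.
- Vaccinated leavers only (6.5.6), if two thirds are vaccinated and carry at the same rate: 590 × 2/3 ≈ 393, and 393/18 ≈ 22 per parameter.

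Sparse data is no reason to omit these factors from the main models.

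**The case against.** The strongest reply is that nothing in the documents shows any of these factors to differ by vaccination status, still less after allowing for the covariates already listed. That stands. A reader might infer that the plan leaves actual confounding in place. The documents support only the possibility.

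A reader might also infer that the omission could create or hide an effect of the size the study seeks. That does not follow. The 20% reduction is set for 2018 v 2019, not for vaccinated v unvaccinated, and neither sex scenario reaches 0.80. Both ratios are also unadjusted. If part of a sex difference in carriage runs through smoking, going out, kissing or alcohol, the existing model already removes some of it.

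The four factors are not equally strong:

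- **Age:** everyone was in year 12 the year before (Protocol 5.1, SAP 2.2), so most of its variation is probably removed by design, despite the 17 to 25 limit.
- **Antibiotics:** the item runs from current use to stopped last month, while SAP 6.1 requires two doses at least one month before the swab for RCT participants to count as vaccinated. Recent use therefore largely follows vaccination and is at most a proxy for something earlier.
- **Smokers at home:** active smoking is already adjusted for.

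The RCT model is not in the documents, so these factors may have been tested and dropped, and the list is not stated to be complete. The RCT is also not a remote population: its year 12 students of 2017 are the leavers of 2018. Finally, SAP 6.3 treats the secondary comparisons as exploratory.

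These points limit the claim but do not rescue the selection rule. Non-significance in the RCT would not rule out confounding here. The plan has already gone beyond its own rule by adding alcohol, and factors named in its own protocol have a comparable claim.

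**Conclusion.** The point holds as a possible, not demonstrated, weakness in the secondary comparisons. The documents establish that the rule in SAP 6.2 does not select confounders, that four collected factors named in the protocol are absent from the list, and that vaccination is not randomised among all leavers. Sex and other smokers at home are the material omissions; age and antibiotics matter less.

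The illustrative size is a ratio of 0.96 to 0.875 with no vaccine effect. It rests on assumed male shares and assumed carriage ratios, before the existing adjustment, and it vanishes if the groups are balanced. The documents do not support reading this as evidence that the primary 2018 v 2019 result is biased.

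**What to change.** In SAP 6.2, add sex and other smokers at home on subject-matter grounds, whatever their p-value in the RCT. Add age and antibiotic use (the four levels in SAP 4.1) on the same basis, at lower priority. Apply the set to 6.4.1, 6.5.1, 6.5.3, 6.5.4, 6.5.6 and 6.5.7, and to genogroup B, genogroup Y and non-groupable in 6.5.2 and 6.5.5 where event numbers allow. Report the four factors by vaccination status, so that a reader can judge whether confounding was a live issue.

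The cost is SAP wording and about 6 model parameters. No new data are needed and the sample size is unchanged. Complete-case analysis under SAP 3.2 would lose slightly more records through missing covariates.
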